(Z1) We will establish prospectively whether usage of cyclic or continuous OCs affects bladder pain sensitivity (on bladder filling test), in women with D+COS compared to women not on OCs. We are adequately powered to detect improvements in bladder pain, assuming a 35% dropout rate (conservative estimate, well exceeding previously published rate of 18-24%^{51,59}) and accommodating a 1:5.2 ratio of non-OC to OC users. We will perform repeated measures ANOVA to determine if experimental bladder pain improves at 6 months compared to baseline in women with D+COS (all having washed out at enrollment). Follow-up results at 12 months will be used to confirm findings. The effect size (f=0.9) was estimated from our preliminary data above. Analyses will be adjusted with E2 and P4 levels as a covariate to determine if the effect of OCs on bladder pain is largely due to its effects on circulating hormones with standard methods⁶⁰.

(Z2) Similarly, we will establish whether among D+COS patients' pelvic hyperalgesia and descending modulation, the hypothesized mechanisms responsible for bladder pain sensitivity, are affected by OC usage. We will perform a repeated measures ANOVA to determine whether significant improvements occur in pelvic hyperalgesia (VAS pain report, and time to normalize), pelvic PPT threshold, bodily PPT thresholds, temporal summation, and CPM in OC treated vs. untreated subjects at 6 and 12 months. Cohen's d's for drugs that affect PPT⁶¹, temporal summation⁶² and CPM⁶³ range between 0.6-0.9.

(Z3) Similar to z1, we will determine if bladder pain sensitivity improves among PBS patients pre- and post-continuous OC exposure using repeated measures ANOVA (6 and 12 months). Although hormonal treatment has been shown to improve bladder pain in 13/15 patients with PBS²³, the exact effect size is not known. Prospectively OC usage has been shown to reduce episodes of urinary calculosis pain (d=0.8)⁶⁴. We are adequately powered to detect an effect size as low as dz=0.6.

(Z4) We will perform ANOVA to determine whether continuous OC usage is superior to cyclic usage for reducing bladder sensitivity, absolute levels of E2/P4, and dysmenorrhea in women with D+COS (6 and 12 mths). Legro and colleagues have established superiority of continuous OC usage over cyclic usage for dysmenorrhea (d=1.6) using a comparable sample size. After surgical removal of endometriosis, continuous OC usage is associated with less non-menstrual pelvic pain than cyclic OC usage (d=0.8)⁶⁵. Our published data^{2,3} suggests a strong relationship between dysmenorrhea and bladder pain. Therefore, we predict a difference of d=0.8 on bladder sensitivity between the groups. If differences are significant, we will evaluate whether any specific nociceptive mechanisms are different between cyclical and continuous OC users by comparing the effects of QST, temporal summation and CPM between groups.

(Z5) To determine whether menstrual, hormonal, central or peripheral changes are most responsible for improvement or worsening of bladder pain, we will use a repeated measures design. We will compare menstrual history, pelvic hyperalgesia, pelvic floor PPTs, external PPTs, CPM, E2/P4 concentrations in D+COS subjects that have >50% improvement in experimental bladder pain to those that have <50% improvement (6 and 12 mths). A similar type analysis showed the effect of duloxetine on CPM in improving diabetic neuropathy (n=30).³¹ If mechanistic differences are comparable to Yarnitsky (d=1.6), we are more than adequately powered with 62 subjects with D+COS accounting for attrition. To confirm the proposed mechanism we will perform multi-level factor analysis. We performed a bootstrap analysis with our hypothesized data set (n=1000 repetitions) and confirmed we can measure 2 independent components (each consisting of 2-5 factors) with 95% certainty (median Kaiser Sampling Adequacy =0.75).

C2.i Expected outcome: We anticipate analyses (z1-z5) will show OC usage reduces bladder pain primarily by restoring descending inhibition via extinguishing menstrual pain. This finding would be consistent with preliminary observations in IBS and PBS.^{9,22,23,59,66} Peripheral sensitivity and circulating hormonal concentrations are expected to have a limited effect as a covariate (z2,3,5). Analysis z4 is expected to show the continuous OC usage is superior to cyclic OC usage for improvement of PBS, in consensus with studies by others on dysmenorrhea and COS.^{22,51} While we have observed a strong relationship between dysmenorrhea and bladder pain^{2,3}, accomplishment of Phase #2 will provide prospective evidence in a randomized controlled trial that bladder pain sensitivity is a modifiable risk factor and understanding of the mechanisms responsible. They will be mailed the ovulation kits to complete before their 6- and 12-month visits.

C2.j Potential Problems: *Differences in OC management within each group:* There will likely be differences in treatments within groups because some participants will require additional OC pills to reduce bleeding, and PBS subjects often rotate medications to treat pain flares. To account for confounding, all deviations will be documented and accounted for as a covariate. We previously confirmed the success of this strategy in our cross-sectional study showing that women on OCs have less bladder sensitivity (see section IV.c.1). Also, women who stop taking the birth control pills but continue as intent-to-treat will not receive their monthly questionnaires on day 15 of each cycle (since presumably discontinuing the pills would shift their cycle). They will continue to receive the monthly questionnaire every 28 days as they would have had they continued the pills.

D. Data Collection and Storage:

Confidentiality: data will be collected by our study coordinator, who has already undergone human subjects protection training and has experience with data handling through our pilot studies. All questionnaire data and data forms will be maintained in REDCap and exported into excel sheets onto a password-protected server as needed for analysis. *The only paper forms used in this study will be the consent and W-9 forms (for payment) containing subject name (no ID), and a study overview checklist, oral contraceptive eligibility checklist, session notes form containing the subject ID only (no name).* Hard copies will be kept in a locked office or cabinet. Electronic data will be coded only with a unique study identifier for participants, linked to a single master list. The phone screen will also be maintained in REDCap and contain PHI. PHI is necessary to collect in order to create an Epic medical record for research participants. At the conclusion of the study, patient identifiers on any hard copies will be blacked out in marker on all data forms.

Quality assurance: *All questionnaires and data forms will be entered using REDCap.* Questionnaire data will be reviewed at the time of each evaluation in REDCap by our research coordinator to ensure all questions are answered and coded appropriately. For pressure-pain threshold, the data acquisition program will automatically save these values. Data will be reviewed and backed up onto the shared drive after each session. Computer parameters will identify potential outliers (using a two standard deviation cutoff) and illogical data, which will be reviewed by the principal investigator. Differences will be reconciled using the session notes form, which will be used to record any applicable extra information which may affect testing (e.g., temperature of room, participant very tired) or any errors that occurred during a session.

Bibliography

1. Zondervan, K. T. *et al.* Chronic pelvic pain in the community--symptoms, investigations, and diagnoses. *Am. J. Obstet. Gynecol.* **184**, 1149–1155 (2001).
2. Tu, F. *et al.* A Non-Invasive Bladder Sensory Test Supports a Role for Dysmenorrhea Increasing Bladder Noxious Mechanosensitivity. *Clinical Journal of Pain* **in press**,.
3. Westling, A. M., Tu, F., Griffith, J. W. & Hellman, K. M. The association of dysmenorrhea with noncyclic pelvic pain accounting for psychological factors. *Am. J. Obstet. Gynecol.* (2013) doi:10.1016/j.ajog.2013.08.020.

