phenotype. An equally critical issue involves identifying which patients would respond best to hormonal treatment. Previous studies have yielded conflicting results on whether OCs improve pain modulation.^{24,25} These studies did not address dysmenorrhea or the usage of continuous OCs, which typically ablate withdrawal bleeding and withdrawal bleed-induced uterine nerve activation. *We hypothesize eliminating a painful stimulus with cyclical OCs will improve descending inhibition and reduce COS. (see Diagram 1)*

To determine whether alterations in pain are due to changes in descending inhibition, spinal cord excitability, or peripheral sensitivity we will use established tests for quantitative sensory testing. Changes in descending inhibition will be tested with conditioned pain modulation (**CPM**).²⁶ CPM involves presenting a counter-stimulus (such as cold water) to one part of the body and then simultaneously measuring the differential sensory response to a noxious stimulus elsewhere. The degree of descending inhibition is quantified by comparing the degree of blunted response from a counter-stimulus compared to the unmatched paradigm. Changes in spinal cord excitability will be tested with temporal summation.²⁷ Temporal summation involves evaluating pain report after repetitive stimulation of pain pathway sufficient to induce increased excitability of dorsal horn neurons. Changes in peripheral sensitivity will be evaluated with mechanical pressure testing. We will perform these tests across multiple body sites to determine whether changes in pain mechanisms are regional or body-wide. Performing these tests will allow us to determine whether eliminating a painful stimulus with cyclical OCs improves descending inhibition, spinal excitability, or overall peripheral sensitivity, which will be done in the Phase 2 protocol. The addition of EEG and EMG recordings will also allow us to determine brain and spinal mechanisms that affect nociceptive modulation.

If OCs are shown to improve descending inhibition, our results will extend prior findings in animals that demonstrate descending inhibition is needed to maintain chronic pain states.¹⁰ In humans, descending inhibition is impaired by repetitive pain insults^{28,29} but normalizes with successful interventions.³⁰ Additionally, our results will establish a relationship between descending inhibition and COS allowing for the development of preventative strategies.³¹

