Since endometriosis and fibroids are identifiable anatomical conditions but understanding of their mechanistic contribution to dysmenorrhea and bladder pain is limited, we will include confirmed endometriosis participants and fibroids participants mixed within our dysmenorrhea

cohort to determine which effects produced by the primary analysis are due to anatomical conditions.

Participants are divided into two arms. Arm #1 participants include women ages 18-45 with dysmenorrhea, women with painful bladder syndrome (PBS), and healthy controls. Arm #2 includes women ages 18-45 with chronic pain or special healthy controls.

Our hypotheses on mechanisms responsible for the transition of menstrual pain to bladder pain will be tested through the following phases:

Phase #1 (includes Arm #1 and Arm #2 participants): *To determine if dysmenorrhea with concomitant bladder pain sensitivity exhibits neurophysiological features consistent with established CPP.* Women with dysmenorrhea without COS and women with chronic pain conditions outside of the pelvic region will be used as controls. Quantitative sensory testing (QST) and a noninvasive bladder pain test we previously have validated will be used to determine whether impairments in descending inhibition and pelvic sensitivity are responsible for vulnerability to COS in women with dysmenorrhea (with and without COS) and/or CPP.

Phase #2 (includes a subset of Arm #1 participants only): *To differentiate the individual contributions of circulating sex hormones and repeated sensitizing events (painful menses) on descending and peripheral mechanisms of bladder pain.* The same QST/bladder pain measures studied in Phase #1 will be retested within the D+COS and PBS subjects following a one-year randomized trial of cyclical vs. continuous OCs vs. no treatment. We added a second option for those who are randomized to Phase 2 that did not want to commit to their randomized group. They will be asked to come in for an additional assessment visit a year later. Participating in the randomized group is preferable but this will allow us to still obtain the follow up data that is important with these participants even if they choose not to participate in their assigned group.

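### Z2 tests the pain mechanisms by pooling cyclic and continuous OC against no OC, and the regimens are compared on mechanisms only if Z4 is significant, so the planned attribution to loss of menstrual pain is not secured

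*Combined protocol and SAP*

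**What the plan says.** Section A gives the aim of Phase 2 as separating the contribution of circulating sex hormones from that of repeated painful menses. Section C2.c randomises women with D+COS to cyclic OC (26), continuous OC (26) or no OC (10). Section C2.b notes that the cyclical group has withdrawal bleeding.

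Section C2.h then plans the following.

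- **Z1 (bladder pain):** whether "usage of cyclic or continuous OCs affects bladder pain sensitivity" compared with women not on OCs, "accommodating a 1:5.2 ratio of non-OC to OC users". There is also an adjustment for E2 and P4.
- **Z2 (pelvic hyperalgesia, pelvic and bodily PPTs, temporal summation, CPM):** compared "in OC treated vs. untreated subjects at 6 and 12 months".
- **Z4:** continuous against cyclic OC on bladder sensitivity, E2/P4 and dysmenorrhea, with d=0.8 predicted for bladder sensitivity. QST, temporal summation and CPM are compared between regimens only if Z4 shows significant differences.
- **Z5:** women with more than 50% improvement in bladder pain against those with less.

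Section C2.i expects Z1 to Z5 together to show that OCs reduce bladder pain mainly by restoring descending inhibition, through the loss of menstrual pain.

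Section A also states: "We hypothesize eliminating a painful stimulus with cyclical OCs will improve descending inhibition and reduce COS". Shortly before, it refers to "the usage of continuous OCs, which typically ablate withdrawal bleeding and withdrawal bleed-induced uterine nerve activation".

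**The concern.** The two OC arms differ in the feature under study: one keeps a regular withdrawal bleed and the other typically does not. Averaging them gives one OC effect that mixes any hormonal action with any benefit from losing the bleed. For bladder sensitivity Z4 supplies the missing regimen comparison. For mechanisms nothing does so unconditionally. If Z4 is not significant, pooled Z2 is the only comparison of randomised arms on CPM and the other mechanisms, and CPM is the measure on which the C2.i conclusion depends.

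Two misreadings are then possible. A positive Z2 could be credited to the removal of menstrual pain when it shows only that taking OCs changed the measure. A null Z2 could be read as no mechanism effect when one exists in the continuous arm alone.

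The section A wording adds to the uncertainty. The hypothesis attaches removal of the painful stimulus to cyclical OCs, while the same section credits continuous OCs with removing the bleed. The reader cannot tell which arm is meant to carry the hypothesis.

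**Working it through.** **1. Is the contrast pooled?** Z2 says so directly. For Z1 it follows from the ratio: (26 + 26)/10 = 52/10 = 5.2, the figure in the Z1 text.

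**2. The plan's own sizes (Table Z, alpha 0.05, power 80%).**

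- Z4: two-sample t-test, d=0.8, two-sided. With 26 per arm power is 80.7%; with 25 it is 79.1%. The requirement is 2 × 26 = 52, as stated.
- Z2: a paired t-test at dz=0.6, two-sided, gives 80.4% power at n=24 and 78.5% at n=23, so 24 reproduces. That calculation describes change within OC users, not the treated v untreated contrast in the Z2 text, so Table Z does not give the power of that contrast.

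**3. What the pooled effect measures.** With equal OC arms, pooled d = (26 × d_cyclic + 26 × d_continuous)/52 = (d_cyclic + d_continuous)/2. A pooled d of 0.8 can arise from 0.8 in both arms or from 0 and 1.6. Z2 alone cannot tell these apart.

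**4. Illustrative power.** Formulas: SE = sqrt(1/n1 + 1/n2) in SD units; noncentrality = d/SE; two-sided noncentral t at alpha 0.05 unless stated.

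- 52 v 10: SE = sqrt(1/52 + 1/10) = 0.345
- 26 v 10: SE = sqrt(1/26 + 1/10) = 0.372
- 26 v 26: SE = sqrt(2/26) = 0.277

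| Contrast | d | d/SE | Power |
|---|---|---|---|
| Pooled v no OC; cyclic 0, continuous 0.8 | 0.4 | 1.158 | 20.7% |
| Continuous v no OC, same case | 0.8 | 2.150 | 55.1% |
| Pooled v no OC; both arms 0.8 | 0.8 | 2.317 | 62.5% |
| One OC arm v no OC, same case | 0.8 | 2.150 | 55.1% |
| One OC arm v no OC, alpha 0.025 | 0.8 | 2.150 | 43.2% |
| Continuous v cyclic | 0.6 | 2.163 | 56.4% |
| Continuous v cyclic | 0.8 | 2.884 | 80.7% |

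The first case assumes that Z4's 0.8 gap carries over to mechanisms. The documents state that gap for bladder sensitivity only.

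For Z1, Table Z's lowest effect is f=.7. Taking d = 2f = 1.4 (the equal-group conversion, so approximate), power is 97.9% pooled and 95.5% per arm. Pooling makes little difference to power there.

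**5. Sensitivity to baseline adjustment.** These are single-time-point tests. Adjusting for a baseline with correlation r multiplies every SE by sqrt(1 − r²). The documents give no r. Assuming r = 0, 0.5 and 0.7 (multipliers 1, 0.866 and 0.714), the first case has 21%, 26% and 36% power pooled, against 55%, 67% and 83% for continuous v no OC. The levels rise and the ordering stays.

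**6. The condition on Z4.** At the plan's own d=0.8, a single Z4 test misses with probability 1 − 0.807 = 0.193. The regimen comparison of mechanisms would then not be run. The text does not say which Z4 outcome or visit must be significant.

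**The case against.** The strongest reply is that C2.h assigns the questions sensibly. It lists three aims: the effect of OCs on bladder pain, whether the regimens differ, and the effect of OCs on mechanisms. OC v no OC is a coherent contrast for the first and third, and Z4 is the sized test of the second. C2.i rests on Z1 to Z5 jointly, and both the E2/P4 adjustment and Z5 address mechanism. This stands to the following extent: a reader might infer that Phase 2 has no test of the hormone-versus-bleeding question, and Z4 shows otherwise for bladder sensitivity. It does not cover mechanisms. E2 and P4 are measured after randomisation, and Z5 compares improvers with non-improvers, so neither is a comparison of randomised arms.

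A reader might also take cyclic v no OC as the pure hormone effect and continuous v cyclic as the pure bleeding effect. The documents do not support either label. The dysmenorrhea inclusion criteria count OCs among the means used to resolve menstrual pain, and C1.d distinguishes withdrawal bleeding from menstruation, so cyclic OC may alter pain as well as hormones. Z4 itself compares E2/P4 between regimens.

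Nor can it be claimed that pooling necessarily costs power in Z2. With equal effects in both arms it gains some.

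Finally, the section A wording might suggest that the hypothesis will be judged on the cyclic arm alone. No planned analysis does that.

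**Conclusion.** The point holds for attribution of mechanism. Z2 pools two arms that differ in the exposure of interest, the regimen comparison of mechanisms depends on Z4, and no planned test sets either OC arm alone against no OC. Under this plan a positive Z2 supports an effect of OCs on mechanisms. It does not support the C2.i statement that the effect comes through loss of menstrual pain. Z1 shares the pooling, but Z4 covers its outcome, and at the effect size assumed for Z1 little power is at issue.

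The size for Z2 is conditional. It runs from a marked loss (21% v 55%) if only the continuous arm works, with a gap of 0.8, to a small gain (62.5% v 55%) if both arms have d=0.8. These figures assume the planned 26, 26 and 10, single-time-point tests and no multiplicity correction. They illustrate the range and do not predict the result.

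The section A wording is a separate inconsistency that needs reconciling. This is a gap in the analysis plan, and the randomised design can already fill it.

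**What to change.** 1. Fit Z1 and Z2 with the three randomised arms as separate levels. Report continuous v no OC, cyclic v no OC and the pooled contrast, which can continue to answer the OC v no OC aims.
2. Compare continuous with cyclic OC on CPM, pelvic hyperalgesia, PPTs and temporal summation whatever Z4 shows. State the power with 26 per arm: 56% at d=0.6 and 81% at d=0.8.
3. Do not label cyclic v no OC a pure hormone effect. Limit the C2.i attribution to what the arm-specific and regimen contrasts jointly support.
4. Reconcile the section A hypothesis with the statement on continuous OCs in the same section, with C2.b, and with the regimen aim in C2.h.
5. Prespecify how the added contrasts are handled for multiplicity.

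The cost is analysis and wording only. The downsides are extra contrasts, an SE about 8% larger per arm (0.372/0.345 = 1.08), and low power against only 10 untreated women: 55% at d=0.8, or 43% with Bonferroni for two contrasts. The arm-specific estimates are worth having for attribution and should be reported with confidence intervals. A non-significant one should not be read as no effect.

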Bladder pain test: All participants will first undergo bladder pain testing described in our validation study². Subjects will be provided directions for the bladder study. The bladder study involves voiding and obtaining baseline measurements of bladder volume with a 3D ultrasound abdominal transducer (GE Voluson 750, Wauwatosa, WI). After hydration with 20 oz of water, subjects are instructed to report when they reach standard levels of bladder urgency: first sensation, first urge, and maximum tolerance and volumetric measurements of the bladder will be made. At each of these time points and every 15 minutes, 0-10 VAS measurements of pain and urgency are recorded. After scanning at maximum tolerance, subjects will urinate in a graded toilet hat to allow for measurement and saving a urinary specimen. Samples will be banked for analyses. If the participant gives permission in the consent form, urine samples will continue to be stored after the study is completed for possible future analyses by our lab on women's health conditions. If the participant does not give permission in the consent form for analyses beyond the current study, their sample will be destroyed upon study completion.

Questionnaires: The previous validated questionnaires from the screening visit will again be employed during the bladder testing. Participants will also complete a handedness questionnaire.

Pressure Pain Threshold Test:

Basic 8: Participants will undergo body and pelvic floor pressure pain threshold testing following the same validated protocols in our published studies^{43,44} using digital external and internal vaginal pressure algometers. The body algometer (for example models see www.paintest.com) is a commonly used hand-held device in pain research that measures the amount of pressure applied to a 1 cm² circular rubber tip. The vaginal algometer consists of 2.5 cm² circular force sensitive resistor, which fits over the pad of the examiner's index finger under an exam glove (Detailed documentation was provided in a separate earlier supplement to the IRB). Prior to evaluation, subjects will report their baseline pain on an NRS 0-10 scale and will be asked to identify any painful body sites.

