The sensory testing will take in total about 20 minutes and will be performed while the participant is connected to EEG.

Additional quality controls: We may need to repeat a task, modify electrode positions, reconfigure equipment, or adjust features in the environment to evaluate the quality of our data acquisition scheme. For example, if a PPT measurement was not obtained or an electrode does not stay put, we may ask the subject to allow us to repeat additional measurements.

All implanted quality controls with permission from the subject will be documented in the subject record.

C1.f Hormone Measurements with Blood (Arm 1 and Arm2): We will ascertain that subjects have not had more than 100 ml of blood drawn over the past 24 hours or 200 ml over the past 30 days. After completion of the pressure/pain testing, a trained nurse or physician will draw up to 60 mL of blood into vacutainers. Separation of serum and plasma will be performed using centrifugation and samples will be aliquoted and banked appropriately to allow for hormone measurements and analyses. To control for the potential influence of reproductive hormones on pain sensitivity, and test our hypothesis about the role of hormonal influences on neurophysiological pain assessments, we will measure serum samples for E2, P4 and testosterone using methods that do not cross-react to the OCs from core laboratories.⁵¹ If the participant gives permission in the consent form, blood samples may also be analyzed for genetics. If the participant gives permission in the consent form, blood samples will continue to be stored after the study is completed for possible future analyses by our lab on women’s health conditions. If the participant does not give permission in the consent form for analyses beyond the current study, their sample will be destroyed upon study completion.

C1.g Follow-up questionnaires: We will ask arm 1 and arm 2 participants to complete an annual follow-up questionnaire including the validated questionnaire instruments mentioned above and a general medical history questionnaire. All arm 1 and arm 2 questionnaires will be

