C2.d Study Visits Participants in Phase #2 will return to repeat experimental pain and sensory assessments identical to the initial Phase #1 and complete the questionnaires referred to in the screening visit plus a side effects questionnaire at six months and one year after OC initiation (which follows a two month washout in Phase #1). These visits should occur on pill days (not cycle days) 7-21 of the cyclical group and any day for the continuous group, which is comparable to cycle days 15-28 in Phase #1. Control subjects not taking OCs will participate during their post-luteal phase days 15-28 (similar to Phase #1). This will make hormonal levels comparable and minimize any vaginal bleeding. For those who are randomized to Phase 2 but decides to not participate in their randomized group, they may be asked to come in a year later for an additional assessment visit to obtain long term follow up data. These participants will be asked to complete daily diaries and ovulation kits for one month prior to the annual assessment visit, similar to Phase 1.

C2.e Home Assessments: Participants in Arm #2 will complete the daily diary during the fifth and eleventh month of OC administration^{33,60}. They will also complete a monthly questionnaire asking questions related to their pain, mental health, and any side effects they may be experiencing (comprised of the McGill Pain Inventory, a side-effects questionnaires, and PROMIS anxiety item bank, PROMIS depression item bank, and PROMIS pain interference item bank). They will not need to do these questionnaires during months 6 and 12 at home because they will do them during their study visit for assessments #2 and #3 respectively. When done at home, they should complete these assessments on or near day 15 of their pill pack for participants on cyclical OCP, day 15 of their menstrual cycle (15 days after their menstrual period started) for participants not taking OCPs, and simply 28 days apart for participants taking continuous OCP.

C2.f Compliance: To evaluate compliance, participants will be asked to return all used and partially used OCP pill packs.

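### Z5 compares improvers with non-improvers on mechanisms measured in the same sessions as bladder pain, so it can show association but not which changes are responsible

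*Combined protocol and SAP*

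**What the plan says.** Section C2.h, analysis Z5, sets the aim as "To determine whether menstrual, hormonal, central or peripheral changes are most responsible for improvement or worsening of bladder pain". For the method it states "We will compare menstrual history, pelvic hyperalgesia, pelvic floor PPTs, external PPTs, CPM, E2/P4 concentrations", contrasted "in D+COS subjects that have >50% improvement in experimental bladder pain to those that have <50% improvement (6 and 12 mths" months in the text. The only models named are a repeated measures design and a multi-level factor analysis. Z5 specifies no lag, no rule on temporal order and no adjustment for randomised arm.

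On timing, C1.e says of assessment visit #1: "All participants will first undergo bladder pain testing described in our validation study". Pressure thresholds, CPM and temporal summation follow in that session. C1.f places the hormone sample later still: "After completion of the pressure/pain testing, a trained nurse or physician will draw up to 60 mL of blood into vacutainers". C2.d says that Phase 2 participants "will return to repeat experimental pain and sensory assessments identical to the initial Phase #1", and fixes those visits "at six months and one year after OC initiation".

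C2.i then anticipates that analyses z1 to z5 together will show that "OC usage reduces bladder pain primarily by restoring descending inhibition".

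**The concern.** Each bladder change and the mechanism change set against it share both the baseline session and the follow-up session. Three things follow.

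- **Shared state.** A bad pain day at baseline or a good one at month 6 moves bladder ratings, pelvic ratings and thresholds together. The baseline visit also selects the women: D+COS status requires a bladder VAS above 15 at assessment visit #1 (C1.a). Some apparent improvement is therefore expected from regression to the mean.
- **Order.** Thresholds and CPM are taken after the bladder test, so a less painful bladder test may itself alter them.
- **Grouping.** The groups are formed by post-randomisation response, so randomisation does not protect the contrast.

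At stake is the mechanistic conclusion. Z5 is a planned comparison with its own row in Table Z and is not labelled exploratory. As written, it could be read as identifying a cause when no mechanism changed, or when pain relief drove the mechanism change.

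**Working it through.** **1. The plan's own figures.** Table Z gives Z5 an effect size of d = 1.6, alpha 0.05, beta 0.2 and a required total of 16. A two-sided two-sample t-test (noncentral t, equal groups) has power 0.785 with 7 per group and 0.845 with 8, so the total is 16, as stated. For attrition at 35%, 95 × 0.65 = 61.75, about 62 (the Z5 text), and 80 × 0.65 = 52 (the Z5 row of Table Z). Text and table differ, so both sizes are used below.

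**2. Shared visit state, no true change.** Assumptions, none of them document figures:
- standardised bladder score at visit t: B_t = √0.7 × trait + √0.3 × e_t (test-retest reliability 0.7);
- mechanism score: M_t = √0.7 × its own trait + √0.3 × f_t, with corr(e_t, f_t) = ρ within a visit and 0 between visits;
- log VAS has SD 0.9, and women are selected above the visit-1 median;
- a woman is an improver if 0.9 × (B_6 − B_0) < ln 0.5;
- Z5 is a t-test of M_6 − M_0 between improvers and non-improvers, 2,000 simulated trials per setting.

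With nothing changing, about 24% of women are classed as more than 50% improved. Rejection rates at nominal 5%, over n = 52 to 62:

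| ρ | Z5 as planned |
|---|---|
| 0 | about 5% |
| 0.2 | 16–18% |
| 0.3 | 31–38% |
| 0.5 | 74–81% |

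Repeat runs under these assumptions scatter by a few points (16–20%, 30–38% and 73–83% in the last three rows). A different set-up, with half the variance visit-specific and about 50% improvers, gave 17–20%, 34–40% and 75–84%, with mean spurious differences of d ≈ 0.29, 0.45 and 0.77.

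**3. A lagged model under the same null.** Regress 12-month bladder VAS on the 0-to-6-month mechanism change, adjusting for baseline and 6-month bladder VAS. In the first set-up it rejects in 3–6% of trials at every ρ. In the second set-up, with baseline mechanism added as a covariate, it rejects in 6–9% at ρ = 0.2 to 0.3 and 14–17% at 0.5. It largely controls visit noise, but not under every assumption.

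**4. Direction.** Set ρ = 0, let all change be complete by month 6 (change SD 0.84 of the baseline SD, coefficient 1.0), and compare the two causal orders:

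| True order | Z5 as planned | Lagged model |
|---|---|---|
| Mechanism drives bladder pain | 91–95% | 43–50% |
| Bladder pain drives mechanism | 91–95% | 44–47% |

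Neither analysis separates the two. In the lagged model a single noisy 6-month VAS does not fully adjust for bladder change, so the 6-month mechanism change acts as a proxy for it.

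**5. Power of the lagged model.** The smallest partial correlation detectable with 80% power is r = tanh[(1.960 + 0.842)/√(n − 3 − k)]. With k = 3 covariates:
- n = 62: tanh(2.802/√56) = 0.36;
- n = 52: tanh(2.802/√46) = 0.39.

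With Bonferroni correction for the six listed mechanism families these become 0.43 and 0.47. A fourth covariate raises each by less than 0.01.

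**The case against.** The strongest reply has four parts.

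**CPM is the least exposed measure.** C1.e defines it by standardised differences before and after the cold-water stimulus in one session, so an additive shift in that day's sensitivity cancels. Simulated that way, false positives were 4–5% for ρ from 0.2 to 0.5. This stands. A reader might infer that the rates in the first table apply to the headline CPM claim; the documents do not support that. Only non-additive state effects or carry-over from the bladder test would reach CPM, and neither can be sized from the documents.

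**A lagged analysis would not settle causation.** This also stands. A reader might infer that the 6- and 12-month schedule lets the trial show which change came first, so that a lagged model should carry the causal claim. Step 4 shows otherwise. The lagged model also loses much power if the effect is complete by month 6, which is the main time point for Z1.

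**The mechanistic case does not rest on Z5 alone.** Z1, Z2 and Z4 compare treatment arms on bladder pain or mechanisms, and menstrual pain is also recorded in month 5 and 11 diaries. It would therefore be wrong to infer that everything in C2.i is unsupported. But arm contrasts show that OCs affect each measure; they do not show that one change produced the other. The off-visit diaries and hormone assays share less pain state than thresholds and ratings, so a ranking of mechanisms is tilted towards the latter.

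**The size is conditional.** The excess is nil at ρ = 0. In addition, a difference near the planned d = 1.6 would exceed the spurious 0.77 seen at ρ = 0.5. Both are fair, but Z5 does not require a difference of that size before a mechanism is credited.

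**Conclusion.** The concern holds in a limited form. Z5 sets a causal question and answers it with a same-session comparison of groups defined by response. Shared pain state can produce false associations, mainly for raw thresholds and pelvic pain ratings: about 16% to 81% per mechanism for an assumed same-day error correlation of 0.2 to 0.5, and about 5% at zero. These rates rest on the assumed reliability, SD and selection rule as well as on that correlation. Independently of it, the comparison cannot distinguish mechanism-driven relief from relief-driven mechanism change. The documents support an associational statement from Z5 and nothing stronger. They support neither extending these rates to CPM nor treating a lagged model as proof of direction.

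**What to change.** 1. In C2.h, label the Z5 improver/non-improver comparison associational, replace the aim of finding what is most responsible, and adjust for randomised arm.
2. In C2.i, remove any causal reading that draws on Z5. The arm comparisons in Z1, Z2 and Z4 can stay.
3. Add as a sensitivity analysis the regression of 12-month first-urge VAS on the 0-to-6-month change in each mechanism, adjusted for baseline and 6-month bladder VAS and arm. Report the reverse lag beside it: 0-to-6-month bladder change predicting the 12-month mechanism.
4. State that the lagged model is meant to control shared visit noise and does not establish direction, because it rejects at similar rates under both causal orders when change is complete by month 6.
5. Reconcile 62 and 52 as the Z5 sample size.

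The cost is wording and two regressions per mechanism on visits already scheduled. The real downsides are a weaker claim from Z5, reliance on women seen at both follow-up visits, and modest power: 80% only for partial correlations of about 0.36 to 0.39 before any multiplicity correction.
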